6.2.1.4 AE within 7 days

Additional analyses restricted to AEs that observed after starting administration of the test drug/comparative drug and up to Analysis Date of Last Dose + 7 days will be defined. If the AE occurs on Day 1 and the onset check box is marked “Onset before first dose of study drug”, then the adverse event will not be considered.

Time to occurrence of event will be calculated (in years) as:

$$(\text{First event date of the given type occurring from Day 1 (post dose) up to Analysis date of minimum of (Last Dose + 7 days, end of safety period)} - \text{Analysis date of first dose intake} + 1) / 365.25$$

With ‘Analysis date of first dose intake’ defined in Section [6.5.4](#) and Analysis Date of Last Dose defined in Section [6.5.3](#)

Subjects who have not experienced an AE for that given type will be censored; the subject will be censored and the time to censoring for these subjects will be calculated (in years) as:

Minimum [Analysis Date of Last Dose + 7 days, **Max** (EOS, Date of Death)] – Analysis date of first dose intake + 1) / 365.25

6.2.1.5 Definition of incidence rate

The incidence rate (per 100 subject years at risk) will be calculated as follows:

$$\frac{\text{Number of subjects with event}}{\text{Total cumulative time at risk (years)}} \times 100$$

Where Total cumulative time at risk is the sum of individual time at risk defined as either time to occurrence of the event or time to censoring for subjects with no event. Time to occurrence of the event and time to censoring are defined in Section [6.2.1.3](#)

Number of subjects at risk is defined as the number of subjects with (censored or non-censored) times to the event of interest greater or equal to t.

6.2.1.6 Definitions of event rate

The event rate (per 100 patient year) during the Safety Emergent Period will be calculated as either:

$$\frac{\text{Number of events}}{\text{Patient Exposure Years}} \times 100$$

Or

$$\frac{\text{Number of subjects experiencing an event}}{\text{Patient Exposure Years}} \times 100$$

Where Patient Exposure Years is defined as [Sum of individual exposure in days (Analysis date of last dose – Analysis date of first dose + 1)] / [(Duration of Safety Emergent Period in days / 365.25)].

The definition used will be indicated in the description of the corresponding analysis in Section [7](#)

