In case that several Hb values are on the same day the average of these values will be used to represent the Hb of that day in the above formula. This calculation will provide the day that the change in Hb value occurs. The number of days that the Hb value has been in each category will be determined and the percentage calculated based on the length of time between the first and last Hb assessment during the evaluated period, i.e.:

Date of Last Hb assessment during the evaluated period – Date of first assessment during the evaluated period.

No imputation will be performed if no Hb value is available in relevant time windows.

In case a subject requires rescue therapy within 6 weeks prior to and during these 8-week evaluation periods, refer to Section 7.11.1 for imputation rules.

Potential Excessive Hematopoiesis (EH), regardless use of rescue therapy, based on Hb central lab will be defined as:

- Hb increase by >2.0 g/dL between any two visits within 4 weeks of treatment during the Efficacy Emergent Period.

Time to first occurrence of potential EH regardless the use of rescue therapy during the Efficacy Emergent Period will be defined in weeks as :

$$(\text{First event date} - \text{Analysis date of first dose intake} + 1) / 7$$

where 'First event date' is defined as first date of occurrence of the criterion met during the Efficacy Emergent Period.

For a subject without potential EH, the time to censoring will be calculated (in weeks) as:

$$\frac{(\text{Date of last hemoglobin assessment during the Efficacy Emergent Period} - \text{Analysis date of first dose intake} + 1)}{7}$$

Refer to Section [6.1](#) and [7.11.6](#) for the definition of the Efficacy Emergent Period.

6.1.3.6 Occurrence (number) of hospitalizations, number of days of hospitalization per patient- exposure -year and time to first hospitalization

The occurrence and the number of hospitalizations per subject during the Efficacy Emergent Period will be calculated.

The number of days of hospitalization per patient- exposure-year (PEY) will be calculated as :

$$\frac{[\text{Sum of the durations of all hospitalizations in days (Minimum ((Date of discharge, End of Efficacy Emergent Period) - Date of admission} + 1)] / [(\text{Duration of Efficacy Emergent Period in days} / 365.25)]}{}$$

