6.1.3.14.4 Work Productivity and Activity Impairment (WPAI: ANS)

The objective of the Work Productivity and Activity Impairment questionnaire: Anemic Symptoms v2 (WPAI: ANS) is to measure work and activity impairment during the past seven days due to anemia. It is self-assessed. The WPAI: ANS consists of 6 questions, including asking if the subject is working, how many hours the person missed work due to anemic symptoms, how many hours the subject actually worked and how the anemic symptoms impacted the productivity and ability to do daily activities (see Appendix [10.4](#)).

For subjects who are currently employed, the following four items will be calculated:

- Percent work time missed due to anaemic symptoms: $100 \times Q2 / (Q2 + Q4)$
- Percent impairment while working due to anaemic symptoms: $100 \times Q5 / 10$
- Percent overall work impairment due to anaemic symptoms: $100 \times Q2 / (Q2 + Q4) + [(1 - Q2 / (Q2 + Q4)) \times (Q5 / 10)]$
- Percent activity impairment due to anaemic symptoms: $100 \times Q6 / 10$

Change from baseline to the average value in weeks 12-28 and in weeks 36-52 will be calculated for these items, following the same rules as defined in Section [6.1.2.4](#) The evaluation period score is defined as the average of available WPAI: ANS subscore of weeks 12-28 (visit at W12 and W28) and weeks 36-52 (visit at W36 and W52).

No imputation will be performed in case of a missing item. Baseline always refers to the assessment at day 1 to be performed prior to first study drug administration.

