7.5.1.3 Event-rates per 100 patient-years

The number of events and event rate (per 100 patient years) during the Safety Emergent Period with TEAEs, as classified by SOC and PT will be calculated by treatment arm. Summaries will be provided for:

- TEAEs
- TEAEs censored at start of chronic dialysis
- TEAE NCI CTC Grades 3 or higher
- Serious TEAEs,
- TEAEs leading to death.

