7.5.1.4 Incidence rates and cumulative incidence

Since the percentage of adverse events might be different between treatment arms due to the difference in the discontinuation rates, in addition to the frequency tables above, the incidence rate (per 100 subject years at risk) and the cumulative incidence at 6 months, 12,

18 months & 24 months with the 95% confidence interval, using Greenwood's formula, will be reported by treatment arm.

It will be done for each of the following event types of special interest:

- Serious TEAEs,
- TEAE for each SOC (>10% for a SOC in total SAF)
- Deaths occurring during the Safety Emergent Period,
- Any death (including post-study follow up period),
- Related serious TEAEs,
- AEs leading to discontinuation of study drug, and
- TEAE NCI CTC Grades 3 or higher.

Hazard ratios of each of the TEAE categories of special interest above will be computed by using Cox Proportional Hazards regression stratified on region and history of CV and adjusted on baseline Hb and baseline eGFR as continuous covariates. Hazard ratios (roxadustat as relative to placebo) and their 95% CI will be calculated for each TEAE category.

As a sensitivity analysis, the above analysis will be repeated using IPCW method (Appendix 10.7) for the following event types of special interest:

- Serious TEAEs,
- TEAE for each SOC (>10% for a SOC in total SAF)
- Deaths occurring during the Safety Emergent Period, and
- TEAE NCI CTC Grades 3 or higher.

A dot-and-forest plot will be produced showing each of the above TEAE categories on the y-axis. The incidence rates by treatment arm, the stratified Cox hazard ratios (roxadustat as relative to placebo) and their 95% CI will be shown on the x-axis.

In addition, cumulative incidence plots for subjects experiencing each of the TEAE categories above will be produced by treatment arm.

Incidence rate (per 100 subject years at risk) in each treatment arm by SOC and PT and the cumulative incidences by SOC will also be produced for the most common TEAEs ($\geq 5\%$ in total SAF). In addition, cumulative incidence plots of subjects experiencing at least one most common TEAEs in a SOC will be produced. A dot-and-forest plot will be produced showing each SOC in the y-axis and the incidence rates, the Cox hazard ratio and its 95% CI in the x-axis. The SOC will be sorted by the hazard ratio.

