7.5.1.5 Sensitivity/Subgroup analyses

- Subgroups of interest :

The number and percentage of subjects reporting TEAEs in each treatment arm will be tabulated by SOC and PT for the subgroups of interest defined in Section 7.8

- Baseline eGFR category (< 15 vs ≥ 15) only :

The following summaries will be provided by comparing Baseline eGFR categories (< 15 vs ≥ 15) :

- Event rate per 100 patient-years for TEAEs by SOC and PT
 - Incidence rate and cumulative incidence for serious TEAEs
 - Incidence rate and cumulative incidence for deaths during the safety emergent period
 - Incidence rate and cumulative incidence for drug-related serious TEAEs
 - Incidence rate and cumulative incidence for AEs leading to discontinuation of study drug
 - Incidence rate and cumulative incidence for TEAE NCI CTC Grades 3 or higher
- Incidence rate and cumulative incidence censoring events occurring on or after the start of chronic dialysis :

The same analysis in incidence as described in Section 7.5.1.4 will be performed (i.e., incidence rate, hazard ratios, dot-and-forest plots and cumulative incidence plots) by censoring all data occurring at initiation of chronic dialysis (see Section 6.2.1.3 for more details regarding the definition of time to event and time to censoring) :

It will be done for :

- Serious TEAEs
- Serious TEAEs by baseline eGFR category (< 15 vs ≥ 15)
- Deaths occurring during the Safety Emergent Period,
- Deaths occurring during the Safety Emergent Period by eGFR category (< 15 vs ≥ 15)
- Drug-related serious TEAEs,
- Drug-related serious TEAEs by eGFR category (< 15 vs ≥ 15)
- AEs leading to discontinuation of study drug,
- AEs leading to discontinuation of study drug by eGFR category (< 15 vs ≥ 15)
- TEAE NCI CTC Grades 3 or higher
- TEAE NCI CTC Grades 3 or higher by eGFR category (< 15 vs ≥ 15)
- Incidence rate for TEAE by SOC and most common PTs
- Cumulative incidence by SOC for most common PTs.

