		
16) Figure added with the comparison between central laboratory hemoglobin (g/dL) and HemoCue hemoglobin (g/dL).
 
17) Removal of the analysis for subjects who have reached Hb \geq 11.0 g/dL prior to week 28.
 
18) For time to first occurrence of serum creatinine doubled compared with baseline, a subject will be counted with an event either for doubled serum creatinine or ESRD, whichever comes first. Otherwise, we censor at date of last non-missing serum creatinine assessment during the Safety Emergent Period.
 
19) For WPAI scale, the number and proportion of employed subjects was summarized by visit and treatment arm.
 
20) Fatigue subscale score added for FACT-An questionnaire.
 
21) Time to All Deaths including Post study FU added.
 
22) Time to AEs by eGFR categories (<15 vs ≥ 15 mL/min/1.73m²) added.
 
23) Number of events and event rate (per 100 patient years) during the Safety Emergent Period with TEAEs added.
 
24) New sensitivity analysis (MMRM) for change to the
	
16) Decision agreed by the study team to check the differences between the two methods.
 
17) Decision agreed by the study team
 
18) Decision agreed by the study team to be consistent with the definition for time to first occurrence of serum creatinine doubled compared with baseline.
 
19) Decision agreed by the study team to check the number of employed subjects by visit and treatment arm.
 
20) Descriptive statistics fatigue were added due to a request from Health Economics and Outputs Research Department.
 
21) Decision agreed by the study team.
 
22) Decision agreed by the study team.
 
23) Decision agreed by the study team to compare treatments in a fair way due to potential difference in exposure between the two arms.
 
24) Decision agreed by the study team.

Version	Date	Changes	Comment/rationale for change
		
average Hb in weeks 28-52 including all Hb values up to end of treatment visit.
 
25) Interaction term baseline*visit added to the main MMRM model for Hb analysis
	
25) Based on internal statistical guidance and check on model fit.

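### SAP 6.2.1.6 divides exposure days by safety-period years, so the denominator of its adverse-event rates per 100 patient-years is not patient-years

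*SAP*

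**What the plan says.** SAP 6.2.1.6 sets the event rate to 100 times the number of events, or of subjects with an event, divided by Patient Exposure Years. The numerator of Patient Exposure Years is the sum over subjects of last dose minus first dose plus 1, in days. The formula continues: "Analysis date of first dose + 1)] / [(Duration of Safety Emergent Period in days / 365.25". The Safety Emergent Period runs from first dose to 28 days after last dose, with caps for the end-of-study visit, death and loss to follow-up (SAP 6.2 and 7.11.5).

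The denominator is used in two places:

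- SAP 7.5.1.3: "The number of events and event rate (per 100 patient years) during the Safety Emergent Period with TEAEs", by SOC and PT, for all TEAEs, TEAEs censored at chronic dialysis, grade 3 or higher, serious and fatal TEAEs.
- SAP 7.5.1.5, for baseline eGFR below 15 versus 15 or above: "Event rate per 100 patient-years for TEAEs by SOC and PT".

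The revision history (SAP 8, version 3.0, item 23) gives the reason for adding these rates: "Decision agreed by the study team to compare treatments in a fair way due to potential difference in exposure between the two arms". Protocol 7.5.1 also plans TEAE rates per subject-exposure-year.

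Two neighbouring definitions are sound. For the incidence rate in SAP 6.2.1.5, "Total cumulative time at risk is the sum of individual time at risk", with each time in years. In SAP 6.1.3.6, "The number of days of hospitalization per patient- exposure-year (PEY) will be calculated as" hospital days divided by the efficacy period in years.

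**The concern.** Elsewhere the SAP turns days into years by dividing by 365.25. Here summed days are divided by a duration already expressed in years, so the result is 365.25 times a ratio of exposure time to safety-period time. The same divisor works for hospitalization because hospital days per year is the quantity wanted there. In 6.2.1.6 it sits inside the definition of the person-time itself.

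At stake are the safety tables meant to make the arms comparable when exposure differs. The SAP expects that it may: 7.5.1.4 gives as its motive "Since the percentage of adverse events might be different between treatment arms due to the difference in the discontinuation rates". A denominator that cancels arm size or exposure can show an excess in one arm where none exists.

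**Working it through.** The documents state no patient-year total or event rate to reproduce, so the check evaluates the formula as written.

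**Inputs from the documents.** Planned allocation 2:1, minimum 300 roxadustat and 150 placebo (SAP 3.3 and 4). Safety period = exposure + 28 days when no cap applies (SAP 6.2).

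**Assumptions.** Exposure by arm is not given. I use mean exposures of 450/450, 500/400, 500/250 and 400/500 days (roxadustat/placebo), every subject in an arm at the mean. The true rate is 100 per 100 patient-years in both arms, with events arising over the safety period. The true ratio is therefore 1.0.

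**Formulas**, for n subjects with d days of exposure:

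- Events = n(d + 28)/365.25.
- A, duration is an arm total: PEY = nd / [n(d + 28)/365.25] = 365.25 d/(d + 28). The n cancels.
- B, duration is each subject's own, then summed: PEY = n × 365.25 d/(d + 28).
- C, one fixed length L: PEY = 365.25 nd/L.

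**Reading A worked at 500/400 days.** Roxadustat: events 300 × 528/365.25 = 433.7; PEY 365.25 × 500/528 = 345.9; rate 125. Placebo: events 150 × 428/365.25 = 175.8; PEY 365.25 × 400/428 = 341.4; rate 51. Ratio 2.44. The true safety-period person-years are 434 and 176.

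| Exposure (days) | A: PEY | A: rates per 100 | A: ratio | B: ratio | C: ratio |
|---|---|---|---|---|---|
| 450 / 450 | 344 / 344 | 114 / 57 | 2.00 | 1.00 | 1.00 |
| 500 / 400 | 346 / 341 | 125 / 51 | 2.44 | 1.22 | 0.99 |
| 500 / 250 | 346 / 328 | 125 / 35 | 3.61 | 1.80 | 0.95 |
| 400 / 500 | 341 / 346 | 103 / 63 | 1.64 | 0.82 | 1.01 |

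**Scale.** Under B the 500-day arm prints 433.7/(300 × 345.9) × 100 = 0.42 per 100 and the 250-day arm 0.23. That is about 240 to 430 times too small. Under C with L = 756 days (728 + 28), a true 100 prints as about 0.6.

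**Range under A.** PEY is 365.25 × 250/278 = 328 at 250 days and 365.25 × 728/756 = 352 at 728 days, whatever the number of subjects.

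**eGFR table under A.** Suppose 60 roxadustat subjects below 15 and 240 at 15 or above (an illustrative split), all at 500 days with equal true rates. The printed rates are 60 × 528/365.25/345.9 × 100 = 25 and, with 240 subjects, 100.

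**Corrected denominators.** Exposure days/365.25 gives ratios of 1.00, 0.99, 0.95 and 1.01 in the four cases. Safety-period days/365.25 gives 1.00 in each, because events were generated over that window.

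**Second calculation on a different basis.** With events generated over exposure time only and 364 days in both arms, A prints about 88 versus 44, again a false doubling.

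**The case against.** The intent is clear. The term is Patient Exposure Years, the rate is per 100 patient-years, and Protocol 7.5.1 plans rates per subject-exposure-year. The divisor resembles the hospitalization formula and may be a drafting carry-over. A programmer may well have used days/365.25, and the documents do not show what was programmed. This stands as far as it goes: the distorted figures describe a literal implementation. But the formula names both exposure and safety-period time, so a programmer correcting it has two candidates and the SAP has to choose.

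The largest ratios need an arm-total divisor, whereas SAP 6.2 and 7.11.5 define the safety period from each subject's own dates. That favours B and makes C the least natural. B still removes the exposure adjustment, although rates of 0.2 to 0.4 per 100 would probably be noticed at the data and table review planned before hard lock (SAP 1). The 328 to 352 range is also not universal: at 100 days the figure is 365.25 × 100/128 = 285, and deaths or loss to follow-up shorten the added 28 days.

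Finally, valid measures run alongside. SAP 7.5.1.4 and 7.5.1.5 give incidence rates for serious, grade 3 or higher, fatal and discontinuation events, several of them by eGFR. This limits the consequence but does not remove it. Incidence rates at PT level in 7.5.1.4 are restricted to common TEAEs (5% or more). Rates that count repeat events, and rates by PT for serious, fatal and less common events, rest on the 6.2.1.6 denominator.

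**Conclusion.** The concern holds. The definition is dimensionally wrong and none of the three readings returns patient-years; that does not depend on any assumption. The size does, because exposure by arm is assumed. With equal true rates, the printed roxadustat/placebo ratio is 1.6 to 3.6 under A and 0.8 to 1.8 under B. Under C it is 0.95 to 1.01 on a meaningless scale. A and B defeat the stated purpose of the tables.

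The scope is limited to the event rates built on 6.2.1.6. These tables carry no test, and no efficacy result, incidence rate, cumulative incidence or hazard ratio changes. It should be fixed because a safety table followed literally could show a spurious doubling.

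**What to change.** Replace the definition in SAP 6.2.1.6 with one of these, and say which:

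- PEY = sum over subjects of (last dose − first dose + 1)/365.25; or
- PEY = sum over subjects of (end of Safety Emergent Period − first dose + 1)/365.25.

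The first matches the name; the second matches the window in which events are counted, and I would prefer it for that reason. In the cases above the choice moves the ratio only between 0.95 and 1.01. For the table censored at chronic dialysis, end each subject's time at the start of chronic dialysis.

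The cost is one formula correction and no new data. SAP 1 allows revisions before hard lock; any change from the planned analyses is to be justified in the CSR.

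A separate, minor correction can go in at the same time. In SAP 6.1.3.14.4, for "Percent overall work impairment due to anaemic symptoms", the factor 100 multiplies only the first term, so Q2 = 0 with Q5 = 5 gives 0.5 instead of 50. It should read 100 × {Q2/(Q2+Q4) + [(1 − Q2/(Q2+Q4)) × Q5/10]}.

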6.2.2 Vital Signs

The following endpoints will be assessed:

- Systolic blood pressure (SBP)
- Diastolic blood pressure (DBP)
- Pulse

In addition, the following assessments will be done:

- Respiratory rate
- Weight

Single measurements for blood pressure (BP) will be taken at three visits during the screening period. Measurements will be taken in triplicate with 2-minute intervals for all other visits. An average will be calculated from the three readings, the average in the eCRF system will not be used.

In case of missing values within a visit, the available readings will be used.

The position and date for the assessment will also be recorded. Change from baseline will be calculated as the measurement taken at the specific visit minus the measurement at baseline visit.

For all vital parameters, the minimum and the maximum post-baseline value during the Safety Emergent Period will be defined. For this calculation, only values from day 2 up to the date of End of the Safety Emergent Period (see Section [7.11.5](#)).

Baseline assessment is the assessment from day 1 visit. If day 1 assessment is missing, screening period assessment will be used in the analysis. For missing visits, the last observation will be carried forward.

From the assessments collected in the ‘Vital Signs - HD/HDF Subjects Only’ form, only the pre-dialysis ones will be used for the classification of analysis visit (see [Table 31](#) Section [7.11.4](#)) and the definition of potentially clinical vital signs criteria.

Vital signs values are potentially clinically significant (PCS) if they meet both the observed value criteria and the change from baseline criteria listed in [Table 6](#) (10 combined criteria).

Table 6 Potentially Clinically Significant (PCS) Vital signs Criteria

Vital Sign Parameter	Flag	Criteria	
		Observed Values	Change from Baseline
Respiratory Rate (breaths per min)	High	≥ 20	Increase of ≥ 5
	Low	≤ 10	Decrease of ≥ 5
Systolic Blood Pressure (mmHg)	High	≥ 170	Increase of ≥ 20
	Low	≤ 90	Decrease of ≥ 20
Diastolic Blood Pressure (mmHg)	High	≥ 110	Increase of ≥ 15
	Low	≤ 45	Decrease of ≥ 15
Pulse (beats per min)	High	≥ 120	Increase of ≥ 20
	Low	≤ 50	Decrease of ≥ 20
Weight (kg)	High	-	Increase of ≥ 10%
	Low	-	Decrease of ≥ 10%

Potentially Clinically Significant Vital Signs Criteria will be calculated at each study visit and on-treatment (at any moment during the Safety Emergent Period) using the worst value among all available measurements.

Time to occurrence of PCS Vital signs:

For each potentially clinically significant vital signs criteria (i.e., 10 combined criteria), the time to occurrence of a PCS at any moment during the Safety Emergent Period (see Section [6.2](#)) will be calculated (in years) as:

$$(\text{First occurrence date} - \text{Analysis date of first dose intake} + 1) / 365.25$$

With ‘First occurrence date’ defined as the first date when both criteria (i.e on observed and change from baseline) are met and Analysis date of first dose intake’ defined in Section [6.5.4](#)

Subjects without abnormality will be censored and time to censoring for these subjects will be calculated (in years) as:

$$(\text{Date of last vital signs assessment where the parameter analyzed is non-missing during the Safety Emergent Period} - \text{Analysis date of first dose intake} + 1) / 365.25$$

Post-dialysis Vital Signs data will be listed and PCS criteria (observed value) only will be evaluated for them and flagged in the listing. No summary tables or Time to Event will be performed for them due to insufficient data.

